8. TRIAL TREATMENTS

8.1. Name and description of investigational medicinal product (IMP)

	Investigational Medicinal Product	Dosage, form and strength
Arm 1	Brensocatib (INS1007)	25mg once daily
Arm 2	Placebo	25mg once daily

Treatment is administered for 28 days in total.

Tablets will be dispensed in bottles containing 35 tablets. Participants will be given the bottle allocated to them on discharge and instructed to take the tablets only for a total of 28 days. Written information, Participant Diary, will be given telling them when to stop taking their tablets. Participants will also be phoned on day 29 as per Schedule of Procedures, at this point they will be reminded that they should stop taking their tablets.

8.2. Regulatory status of the drug

No marketing authorisation

8.3. Product Characteristics

Brensocatib is a film-coated, oral tablet available in a dose strength of 25 mg. The tablets are round, biconvex, brown film-coated tablets. The tablets are an immediate-release dosage form with rapid dissolution characteristics under in vitro test conditions. Each tablet contains active ingredient Brensocatib and the following inactive US Pharmacopeia/National Formulary or European Pharmacopoeia compendia ingredients: microcrystalline cellulose, dibasic calcium phosphate dihydrate, sodium starch glycolate, silicon dioxide, and glyceryl behenate. The tablet is film coated with hypromellose, polyethyleneglycol, titanium dioxide, iron oxide red, iron oxide yellow, and iron oxide black.

Matching Placebo

The matching placebo tablet contains microcrystalline cellulose and sodium stearyl fumarate and is coated identically to Brensocatib tablets.

8.3.1. Packaging and Labelling Information

Brensocatib and matching placebo will be packed in individual high-density polyethylene bottles, labelled and stored as described below.

Labels will be prepared in accordance with Good Manufacturing Practice Annex 13 requirements and local regulatory guidelines. The trial drug label on the bottle specifies the appropriate storage.

8.3.2.Storage

All trial drug supplies must be stored in accordance with the label information. Until dispensed to the trial participants, the trial drugs will be stored at room temperature between 2°C and 30°C, at the sites in a securely locked, limited access storage area under appropriate storage conditions, accessible to authorized personnel only.

8.4. Accountability Procedures

All IMP will be supplied by Insmed Incorporated. Trial medication will be received by a delegated person at the trial site Clinical Trial Pharmacy, handled and stored safely and properly, and kept in a secured location as detailed in the IMP Management Plan. All trial clinical supplies will be dispensed only in accordance with the protocol.

The PI or delegated trial staff will maintain an accurate record of the receipt and dispensing of the IMP in a drug accountability log. Monitoring of drug accountability will be performed as per Sponsor Monitoring Plan. Clinical staff will be asked to return all unused medications and packaging at the end of the trial or at the time of discontinuation of treatment. When discharged participants will be given a stamped addressed envelope to return unused IMP to trial staff. On return of the medicines, the trial staff will perform a check of returns and this will be recorded on the drug accountability log. Unused treatment will be disposed of by the Clinical Trial Pharmacy as per local Standard Operating Procedure. Non returned IMPs will be recorded by clinical trials pharmacy staff as per the IMP management plan.

8.5. Preparation and labelling of Investigational Medicinal Product

Preparation and labelling of trial medication will be performed by Insmed Inc. with annex 13-compliant labels. Trial medication will be supplied to Sharp Clinical Service (UK) Ltd who will act as Importer of Record for the Sponsor. Sharp will be responsible for distribution of trial medication to trial sites.

8.6. Drug storage and supply

Will be detailed in a trial IMP Management Plan.

8.7. Dosage schedules

Route of administration: oral. Where a participant is unable to take oral medication they will be excluded from the trial. If during the treatment phase a participant becomes unable to take oral medication their treatment will be given by nasogastric tube (NGT) where the participant has this in place for clinical reasons. After crushing, the tablet should be placed in water for 5-10 mins, after pushing through NGT, flush with 10 mL of water (or saline), and clamp NGT for 30 mins.

Frequency of administration: once daily, before breakfast. On day of randomisation the first dose may be given up to 5pm, after that point the first dose should be given the following day before breakfast. The day of first dose received will be deemed to be day 1 of the trial.

Missed doses: if a dose is missed this should be given within 10 hours of the missed dose.

Maximum duration of treatment: 28 days. Where a participant misses a dose due to being unable to take oral medication, or for any other reason, the treatment duration will not be extended.

8.8. Dosage modifications

No changes to dosage or regimen will be made during the course of the trial

8.9. Known drug reactions and interaction with other therapies

Results of prior studies indicate that there was little or no effect of a strong CYP3A4/5 inhibitor (itraconazole) on the exposures of Brensocatib. However, co-administration of inhibitors of more than 1 INS1007 elimination pathway (e.g. CYP3A4/5 with CYP2C8 and/or CYP2D6 inhibitors) should be cautioned as there is no information on the combined interaction potential. For this reason we have excluded patients taking strong CYP3A4/5 inhibitors with the exception of clarithromycin or other macrolide antibiotics. Macrolides were permitted in the phase 2 "Willow" trial of Brensocatib (INS1007)

8.10. Concomitant medication

Details of concomitant medications will be recorded on the trial eCRF on a concomitant medications form.

8.11. Trial restrictions

Participants should take their usual medication as well as any other medications prescribed for treatment of COVID-19 as directed by their clinical team. No concomitant medications will be stopped for trial enrolment purposes.

Participants should not be prescribed Itraconazole, Ketoconazole, diltiazem, verapamil, phenytoin, rifampicinprotease/integrase inhibitors or non-nucleoside reverse transcriptase inhibitors whilst taking trial medication. The Liverpool HIV checker (https://www.hiv-druginteractions.org/checker) can be used to check for interactions. Simvastatin should be used as a surrogate for Brensocatib as it metabolised similarly by CYP 3A4. It will be a clinical decision by the PI as to whether trial drug or restricted drug is stopped.

Females of childbearing potential and males must be willing to use a highly effective method of contraception (hormonal or barrier method of birth control; abstinence). Contraception should be continued until at least 30 days after final dose of IMP taken. Such methods include:

- combined (estrogen and progestogen containing) hormonal contraception associated with inhibition of ovulation:
 - o oral
 - intravaginal
 - transdermal
- progestogen-only hormonal contraception associated with inhibition of ovulation
 - o oral
 - o injectable
 - implantable
- intrauterine device (IUD)
- intrauterine hormone-releasing system (IUS)
- bilateral tubal occlusion
- vasectomised partner
- sexual abstinence

8.12. Assessment of compliance with treatment

Trial drug compliance will be assessed by trial staff in hospitalised participants by checking drug returns and medication record sheet. The PI or delegate will collect unused medication and packaging from the clinical team. Where participants are discharged from hospital during the treatment phase, returns will not be requested, trial staff will ask participants at the day 29 phone call how many tablets are remaining and this will be recorded on the accountability log. Trial drug compliance will be assessed from the information provided by the participant and the above medication checks

8.13. Name and description of each Non-Investigational Medicinal Product

N/A

9. PHARMACOVIGILANCE

9.1. Definitions

Term	Definition
Adverse Event (AE)	Any untoward medical occurrence in a participant to whom a medicinal product has been administered, including occurrences which are not necessarily caused by or related to that product.
Adverse Reaction (AR)	An untoward and unintended response in a participant to an IMP which is related to any dose administered to that participant.
	The phrase "response to an IMP" means that a causal relationship between a trial medication and an AE is at least a reasonable possibility, i.e. the relationship cannot be ruled out.
	All cases judged by either the reporting medically qualified professional or the Sponsor as having a reasonable suspected causal relationship to the trial medication qualify as ARs. It is important to note that this is entirely separate to the known side effects listed in the SmPC. It is specifically a temporal relationship between taking the drug, the half-life, and the time of the event or any valid alternative etiology that would explain the event.
Serious Adverse Event	A SAE is any untoward medical occurrence that:
(SAE)	 results in death is life-threatening requires inpatient hospitalisation or prolongation of existing hospitalisation results in persistent or significant disability/incapacity consists of a congenital anomaly or birth defect Other 'important medical events' may also be considered serious if they jeopardise the participant or require an intervention to prevent one of the above consequences.
	NOTE: The term "life-threatening" in the definition of "serious" refers to an event in which the participant was at risk of death at the time of the event; it does not refer to an event which hypothetically might have caused death if it were more severe.
Serious Adverse Reaction (SAR)	An adverse event that is both serious and, in the opinion of the reporting Investigator, believed with reasonable probability to be due to one of the trial treatments, based on the information provided.
Suspected Unexpected Serious Adverse Reaction (SUSAR)	A SAR, the nature and severity of which is not consistent with the information about the medicinal product in question set out in the reference safety information.

NB: to avoid confusion or misunderstanding of the difference between the terms "serious" and "severe", the following note of clarification is provided: "Severe" is often used to describe intensity of a specific event, which may be of relatively minor medical significance. "Seriousness" is the regulatory definition supplied above.

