9.3. Recording and reporting of SAEs, SARs AND SUSARs

AEs will be recorded on the AE Log in the eCRF and will be assessed for severity and causality by the CI or PI. AEs occurring from the time a participant consents to join the trial until the participant's day 29 will be recorded. An AE may be classified as a SAE or AR. An initial assessment of expectedness/listedness for SAEs will be conducted by the PI based on the Reference Safety Information (RSI).

Participants discharged from hospital before the end of trial will be given a diary to record adverse events, this will be used as an aide memoire for them to report AEs at the telephone follow-up call. This diary will not be returned to the trial staff.

The PI will make a clinical judgment as to whether or not an AE is of sufficient severity to require the participant's discontinuation of treatment. A participant may also voluntarily discontinue treatment due to what he or she perceives as an intolerable AE. If either of these occurs, the participant should be given appropriate care under medical supervision until symptoms cease, or the condition becomes stable.

AEs and SAEs will be followed up until recovered/recovered with sequelae/death or for 30 days after participant's day 29 whichever happens first. SUSARS will be followed until resolution.

The CI, PI or delegate will check the medical records for the occurrence of AEs and hospitalisations at every data collection point/telephone call during the trial. Serious AEs (SAEs) will be submitted on an SAE form to the Sponsor Pharmacovigilance Section [contact] within 24 hours

of becoming aware of the SAE. All SAEs need to be assessed and signed off by the PI or a delegated doctor within the 24hr reporting window. Site PIs will also notify the CI when submitting an SAE.

The evaluation of expectedness will be made based on the knowledge of the reaction and the relevant safety information (RSI) in the Brensocatib Investigators Brochure (IB) (see section 9.4). The Sponsor will make the definitive assessment on expectedness for the purposes of SUSAR reporting.

The Sponsor is responsible for reporting SUSARs to the UK competent authority, the MHRA, and the Research Ethics Committee (REC). Fatal or life threatening SUSARs will be reported within 7 days and non-fatal and non-life threatening SUSARs within 15 days.

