**Pruritus** 

Pulmonary embolism

Pulmonary hypertension

Pyrexia

Rash

Rash macular

Rash papular

Rash pruritic

Rash pustular

Sinus bradycardia

Steroid diabetes

Subcutaneous emphysema

Suicidal ideation

Swelling face

Syncope

Thrombosis

Tongue discolouration

Toothache

Transaminases increased

Urinary tract infection

Urosepsis

Vision blurred

Vomiting

Table 14: Summary of all adverse events - descriptors

	Brensocatib	Placebo	Total
Severity	N =	N =	N=
No Information			
Mild			
Moderate			
Severe			
Total			
Relationship to Trial Drug			
No Information			
None			
Possible			
Probable			
Total			
Action taken			

	No Information
	None
	Hospitalisation
	IMP temporarily stopped
	IMP permanently stopped
	Con meds commenced
	Other (specify)
	Hospitalisation, Con meds commenced
	IMP temporarily stopped; IMP permanently stopped
	IMP permanently stopped; Con meds to commenced
	Total
Outco	me
	No information
	Recovered
	Recovering
	Not recovered
	Unknown
	Fatal
	Total

Table 15. Additional treatments

Additional treatments	Brensocatib	Placebo
	N =	N =
Co-enrolment in RECOVERY		
Co-enrolment in REMAP-CAP		
Co-medications:		
Antibiotics		
Azithromycin		
Corticosteroids		
Convalescent plasma		
Hydroxychloroquine		
Lopinavir-Ritonavir		
Remdesivir		
Tocilizumab

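### Protocol 9.1 sets a stricter causality test, with fewer judges, for a serious adverse reaction than for an adverse reaction, so read literally some serious unexpected reactions fall outside SUSAR reporting

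*Protocol*

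**What the plan says.** The table in Protocol section 9.1 defines three linked terms.

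- **AR.** The test is that "a causal relationship between a trial medication and an AE is at least a reasonable possibility, i.e. the relationship cannot be ruled out". On who decides, the row covers "All cases judged by either the reporting medically qualified professional or the Sponsor as having a reasonable suspected causal relationship" to the trial medication.
- **SAR.** The row starts from an adverse event, not from the AR defined above it. It asks that the event be serious and, "in the opinion of the reporting Investigator, believed with reasonable probability to be due to one of the trial treatments".
- **SUSAR.** This is "A SAR, the nature and severity of which is not consistent with the information about the medicinal product in question", as set out in the reference safety information.

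Section 9.3 gives the causality assessment to the CI or PI. On the Sponsor's part it says: "The Sponsor will make the definitive assessment on expectedness for the purposes of SUSAR reporting". It gives the Sponsor no matching role on causality.

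**The concern.** A serious adverse reaction should be an adverse reaction that is serious. Here the two rows differ twice: in the strength of belief required (possibility against probability) and in whose belief counts (clinician or Sponsor against the investigator alone). An event can therefore be serious and be an adverse reaction without being a serious adverse reaction.

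This matters because the SUSAR label triggers actions that the AR and SAE labels do not:

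- reporting to the MHRA and the ethics committee within 7 days (fatal or life-threatening) or 15 days (others), under 9.3 and Appendix 5;
- notification of site investigators by the CI, under 9.5;
- follow-up until resolution, where follow-up of other AEs and SAEs ends no later than 30 days after the participant's day 29, under 9.3 and 9.10.

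The product has no marketing authorisation (8.2), and the patient experience that the protocol describes is in bronchiectasis (section 2, Appendix 1). In hospitalised COVID-19 the disease itself will often offer another explanation for a serious event, so a judgement of possible but not probable is foreseeable.

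**Working it through.** No arithmetic applies. The check has two steps: apply the definitions as written, then look for text elsewhere that reconciles them.

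**Step 1. Apply the three rows of 9.1.** Take a serious event that is not consistent with the reference safety information, and vary only the causality judgement.

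| Causality judgement | AR | SAR | SUSAR |
|---|---|---|---|
| Investigator believes it with reasonable probability | yes | yes | yes |
| Investigator thinks it only reasonably possible | yes | no | no |
| Investigator does not suspect it, Sponsor does | yes | no | no |
| Neither suspects it | no | no | no |

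The second line follows from the difference in threshold. The third follows from the difference in judge, and needs no view on what reasonable probability means. In both, the SUSAR answer is no because a SUSAR must first be a SAR.

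**Step 2. Look for a reconciling rule.**

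- *9.2* sends SAEs and SARs to the Sponsor, with stated exclusions. It does not define causality.
- *9.3* gives causality to the CI or PI, and the Sponsor's definitive role is limited to expectedness.
- *9.5* gives causality to the PI, and to the CI where no local medical assessment could be obtained. The Sponsor's listed task is to review SUSARs, which presupposes that the label has already been applied.
- *9.6* requires all deaths to be reported to the Sponsor whatever the cause. That is SAE reporting, not SUSAR classification.
- *9.10* sets follow-up for ARs and SUSARs and does not say how a serious AR becomes a SUSAR.
- *Appendix 5* has the PI or delegate review causality and the Sponsor review SAEs within 24 hours of receiving the form. It states no route by which the Sponsor's own suspicion changes the classification.

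None of these reconciles the two rows.

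**The case against.** The strongest reply is that little depends on the label. Apart from the exclusions in 9.2, SAEs go to the Sponsor within 24 hours of the site becoming aware, whatever their causality. The Sponsor reviews them within a further 24 hours. All deaths are reported, and an independent DMC reviews AEs, SAEs and laboratory data unblinded (2.1, 9.5). A sensible site or Sponsor might also simply treat any serious AR as a SAR.

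Much of this stands. For events in the recording window, which runs to day 29, capture and oversight do not depend on the SAR row. What it does not answer is expedited reporting: none of these safeguards turns an event that fails the SAR row into a SUSAR. Sensible practice may fill the gap, but it would do so against the text of 9.1.

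A reader might also infer more than the documents support:

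- *That every serious event graded Possible is barred from being a SUSAR, so that one of the two positive grades is lost.* SAP Table 14 lists Possible and Probable under "Relationship to Trial Drug", but it is a reporting shell for all adverse events. Neither document ties its grades to the two thresholds in 9.1. The link is a natural guess, not a rule, and gives no proportion.
- *That analysed counts of related serious events would depend on which row a site applied.* The SAP plans no such count. It analyses SAEs regardless of causality and lists deaths and SAEs.
- *That this is the drug's first use in acutely ill patients.* The documents do not say so.

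**Conclusion.** The concern holds as an internal inconsistency in the safety definitions. Nothing suggests that the stricter SAR test was a deliberate design choice. Its reach is two classes of serious unexpected event: those judged only reasonably possible, and those suspected by the Sponsor alone. The effect is confined to classification and to what follows from the SUSAR label. It touches no endpoint, analysis population or sample size.

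The size in events cannot be given, because the documents contain no counts of serious events by causality. The conclusion rests on reading 9.1 literally and on taking reasonable probability to be a higher bar than reasonable possibility. The second class needs only the literal reading. It should be corrected because the text governs regulatory reporting for an unlicensed product. The routine flow of SAEs to the Sponsor and the DMC limits the harm.

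**What to change.** Make two changes to the protocol.

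1. In 9.1, define a SAR as any adverse reaction, as defined in the AR row (same threshold, same judges), that meets one of the seriousness criteria.
2. In 9.3, state that causal suspicion by either the investigator or the Sponsor is enough for SAR and, if the event is unexpected, SUSAR classification. This puts into operation what the AR row already says about who may judge.

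The SUSAR row can stay as it is, since it will then build on the corrected SAR row. The SAP needs no change on this point. The cost is about two sentences in an amendment, a note to sites and possibly a few more expedited reports.

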9.2. Operational definitions for (S)AEs

Deterioration of the existing condition, COVID-19, with the exception of death, or known side-effects recorded as primary or secondary endpoints are not reported as (S)AEs or (S)ARs but are recorded separately. All events resulting in deaths will be reported as SAEs.

The following events will be deemed as expected in participants with COVID-19 and will not be recorded as AEs:

- cough
- pyrexia
- headache
- tiredness
- diarrhoea
- aches and pains
- nasal congestion
- runny nose
- sore throat
- Anosmia
- Loss of taste
- deterioration in renal and or liver function and changes in full blood count parameters; these will be recorded as endpoints for the evaluation of safety of the IMP

Anticipated AEs for the trial drug are be listed in the Reference Safety Information these would not be considered to be SUSARs unless the severity of the event was considered to be unexpected.

All SAEs and SARs will be reported to sponsor, see section 9.3, with the exception of hospitalisation as this is recorded as an end point.

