3.7. Table of endpoints/outcomes

Objectives	Outcome Measures	Timepoint(s)
Primary Objective Participant clinical status (on a 7- point ordinal scale) In accordance with WHO recommendations the primary endpoint will be determined by a pilot trial of the first 100 participants.	 7-point ordinal scale: Not hospitalised, no limitations on activities Not hospitalised, limitation on activities; Hospitalised, not requiring supplemental oxygen; Hospitalised, requiring supplemental oxygen; Hospitalised, on non-invasive ventilation or high flow oxygen devices; Hospitalised, on invasive mechanical ventilation or ECMO (Extracorporeal membrane oxygenation) Death. 	Up to day 29
Secondary Objectives	Outcome Measures	Timepoint(s)
Evaluate the clinical efficacy of Brensocatib relative to standard care in adult patients hospitalised with COVID-19	Clinical Severity Time to an improvement of one category from admission using 7-point ordinal scale. Participant clinical status on 7-point ordinal scale Mean change in the 7-point ordinal scale	Daily whilst hospitalised Days 3, 5, 8, 11, 15 and 29. Baseline to days 3, 5, 8, 11, 15 and 29.
	National Early Warning Score (NEWS): Time to discharge or to a NEWS of ≤ 2 and maintained for 24 hours, whichever occurs first. Change from baseline Oxygenation:	Daily whilst hospitalised Days 8, 15, 29
	Oxygen free days Incidence and duration of new oxygen use during the trial	1-29 days 0-29 days
	Mechanical Ventilation: Ventilator free days	1-29 days

	Incidence and duration of new mechanical ventilation use during the trial.	1-29 days
	Hospitalisation:	
	Duration of hospitalisation (days).	Date of admission and discharge
	Mortality:	
	28-day mortality	Date of death
Evaluate the safety of the	Cumulative incidence of SAEs	1-29 days
intervention through 28 days of follow-up as compared to the control arm	Discontinuation or temporary suspension of treatment	1-29 days
	Changes in white cell count, haemoglobin, platelets, creatinine, total bilirubin, ALT, and AST over time (hospitalised participants only)	Days 0/1, 3, 5, 8, 11, 15, 29
	Adverse events of special interest- hyperkeratosis, infections and dental complications	1-29 days
	dental complications	
Exploratory Objectives	Outcome Measures	Timepoint(s)
Exploratory Objectives Evaluate the virologic efficacy of Brensocatib	·	Timepoint(s) Day 15 and day 29

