7.11. Withdrawal criteria

Participants are free to withdraw at any time and are not obliged to give a reason(s). The CI, PI or delegate will make a reasonable effort to ascertain the reason(s), both for those who express their right to withdraw and for those lost to follow-up, while fully respecting the individual's rights.

The PI may withdraw a participant at any time if it felt to be in the best interest of the participant and treatment continuation would be detrimental to the participant's wellbeing. In addition, the trial drug will be discontinued in the following circumstances:

- Persistent adverse effects which are determined to be severe, persistent, treatment-related and not responsive to treatment
- If an allergic reaction to trial drug occurs, the trial drug will be stopped and treatment will be initiated as appropriate
- Absolute neutrophil count less than 1.0 x 10⁹ cells per L at any time.

A full explanation for discontinuation of trial drug will be provided to the participant. As the trial is being conducted on an intention to treat basis, if the participant has been randomised and given one or more dose of IMP, s/he will be asked to complete trial assessments as per the protocol, if the CI/PI considers it appropriate, to allow for an intention to treat analysis, but will be censored in the per-protocol analysis. Participants are free to refuse to do so. Withdrawn participants will not be prescribed trial drug.

Those withdrawn, including those lost to follow-up, will be identified and a descriptive analysis of them provided, including the reasons for their loss, if known, and its relationship to treatment and outcome.

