## Oxygenation

No of days free from oxygen

Duration of new oxygen use

Mechanical ventilation

Number of patients receiving new mechanical ventilation

No of days free from ventilation

Duration of new ventilation used

Duration of hospital stay - days

28-day mortality

Table 10: Safety analyses

	Brensocatib N =	Placebo N =	Effect estimate (95% CI)
% of patients with at least 1 AE			
Incidence of SAEs			
Discontinuation or temporary suspension of treatment			
Changes in white cell count			
Changes in haemoglobin			
Changes in platelets			
Changes in creatinine			
Changes in total bilirubin			
Changes in ALT			
Changes in AST			
Adverse events, n (%):			
Hyperkeratosis (Skin)			
Infections			
Dental complications			

Table 11: Adverse Events

Adverse Event - n (%)	Brensocatib	Placebo
	N =	N =
Death		
Life-threatening		
Required hospitalisation		
Resulted in persistent or significant disability		
Medically significant		
Total		

Table 12: Summary of all adverse events - System Organ Class Level

N = N =	Total	Placebo	Brensocatib
	N=	N =	N =

Number of participants

Number of participants with adverse events

Number of participants without adverse events

Number of adverse events

Cardiac disorders

Eye disorders

Gastrointestinal disorders

General disorders and administration site conditions

Infections and infestations

Injury, poisoning and procedural complications

Investigations

Metabolism and nutrition disorders

Musculoskeletal and connective

tissue disorders

Nervous system disorders

No Code

Psychiatric disorders

Renal and urinary disorders

Respiratory, thoracic and mediastinal disorders

Skin and subcutaneous tissue

disorders

Vascular disorders

Table 13: Summary of all adverse events - Preferred Term Level

Brensocatib	Placebo	Total
N =	N =	N=

Number of participants

Number of participants with adverse

events

Number of participants without adverse

events

Number of adverse events

Abdominal discomfort

Abdominal pain

Acute kidney injury

Arthralgia

Back pain

Blood glucose increased

Bradycardia

Cerebrovascular accident

Chest discomfort

Chest pain

Clostridium difficile infection

Constipation

Cough

Delirium

Diarrhoea

Dizziness

Drug eruption

Dry mouth

Dry skin

Dysarthria

Dyspepsia

Dyspnoea

Dysuria

Electrocardiogram abnormal

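### Protocol 9.2 keeps eleven listed symptoms out of AE recording with no exception for drug-related or serious cases, which conflicts with 9.1 and SAP Table 13

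*Protocol*

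**What the plan says.** Protocol section 9.2 introduces its list with "The following events will be deemed as expected in participants with COVID-19 and will not be recorded as AEs". The list names eleven symptoms: cough, pyrexia, headache, tiredness, diarrhoea, aches and pains, nasal congestion, runny nose, sore throat, anosmia and loss of taste. A twelfth bullet covers renal, liver and blood count changes, for which the section adds that "these will be recorded as endpoints for the evaluation of safety of the IMP". No bullet is limited by relatedness to trial drug or by seriousness.

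The opening sentence of 9.2 says that "known side-effects recorded as primary or secondary endpoints are not reported as (S)AEs or (S)ARs but are recorded separately". Its closing sentence says that every SAE and SAR goes to the sponsor, with hospitalisation the only exception. Section 3.7 includes among the secondary outcomes "Adverse events of special interest- hyperkeratosis, infections and dental complications".

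The SAP contains "Table 13: Summary of all adverse events - Preferred Term Level", with rows for Cough, Diarrhoea, Headache and Pyrexia. SAP 10.2 brings every reported AE into the summaries. SAP 14 reports no changes to the protocol.

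**The concern.** The listed symptoms are typical of COVID-19, but some of them, such as headache and diarrhoea, could also be caused by a drug. Once they are barred from the AE Log, nobody is asked to judge whether a given case was caused by brensocatib. The SAP then tabulates and compares AEs as if they had been fully collected.

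At stake is the tolerability comparison. The proportion of participants with AEs is compared between arms (SAP section 10), heads SAP Table 10, and is a safety endpoint of the preliminary analysis (SAP 7.6). A reader of Table 13 could take an empty or sparse headache row as evidence of good tolerability when it reflects the recording rule. For serious events of special interest, the question is whether they enter SAE incidence, which is itself a safety outcome.

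**Working it through.** The documents state no figure here, so the check compares the rules with one another and matches terms.

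**1. Recording rules side by side**

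| Place | Rule | Effect on a non-serious, drug-related headache |
|---|---|---|
| Protocol 9.1 | Any untoward occurrence is an AE; one with a reasonably suspected causal link is an AR | AE and AR |
| Protocol 9.2 | Listed symptoms are not recorded as AEs | Not recorded |
| Protocol 9.3 | Logged AEs are assessed for severity and causality; an AE may then be classed as an SAE or AR | No entry to assess |
| Protocol Appendix 5 | The PI reviews recorded AEs for causality and seriousness | No entry to review |
| SAP 10.2 | All reported AEs are summarised | Absent |
| SAP Table 13 | Has a Headache row | Row provided, no rule for it |

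The working route to AR or SAE status starts with a recorded AE. The closing sentence of 9.2 therefore does not settle what happens when a listed symptom turns serious: it requires SAEs to be reported but does not say that such a symptom is one.

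**2. Overlap with SAP Table 13**

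The table has 88 term rows, or 87 without No Code.

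- Exact matches to the symptom list: Cough, Diarrhoea, Headache, Pyrexia = 4.
- By judgement: Arthralgia, Back pain, Musculoskeletal pain, Pain and Pain in extremity (aches and pains), and Pharyngitis (sore throat) = 6.
- Matching the laboratory bullet: Acute kidney injury, Liver function test abnormal and "Transaminases increased" = 3.

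The total is 4 + 6 + 3 = 13 of 87, of which only 4 are certain. If 9.2 is followed, those four rows can hold serious events at most.

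**3. Direction of the effect**

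Let p0 and p1 be the proportions with a non-serious listed symptom on placebo and brensocatib, and c the share that reaches the AE Log, equal in both arms because staff are blind.

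- Recorded proportions are c·p0 and c·p1. For c > 0 the ratio p1/p0 is kept, and the difference shrinks to c·(p1 − p0).
- With 9.2 followed literally, c = 0, giving 0 v 0 and no comparison.
- For the proportion with any AE, let q be the proportion with some other AE, equal in both arms and independent of the listed symptom. The true difference is (1 − q)(p1 − p0). With c = 0 the recorded difference is q − q = 0.

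The documents give none of p0, p1, q or c, so only the direction can be stated.

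**4. Events of special interest**

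Hyperkeratosis, infections and dental complications are secondary outcomes in 3.7 and monitored risks in Appendix 1. So far as they count as known side-effects, the opening sentence of 9.2 removes them from SAE and SAR reporting, while the closing sentence requires any serious case to be reported. Both cannot hold for the same event.

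**The case against.** Exempting symptoms of the disease under study, in acutely ill inpatients, is a reasoned choice that avoids a log full of background events. That stands as a reason for an exemption, but does not explain why drug-related cases are included in it.

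Several stronger readings are tempting, and the documents do not support them:

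- **Known side-effects are barred in general.** Only those that are endpoints are moved, and they are recorded separately. Events of special interest have their own rows in SAP Table 10. The sentence on anticipated drug events says "these would not be considered to be SUSARs unless the severity of the event was considered to be unexpected", which concerns SUSAR status rather than recording.
- **Severe or serious events disappear.** Deaths remain SAEs, and 9.2 says that SAEs and SARs are reported. For a serious listed symptom the text is ambiguous; it is not a bar.
- **The stopping criterion cannot work.** Section 7.11 refers to "Persistent adverse effects which are determined to be severe, persistent, treatment-related and not responsive to treatment". That is a clinical determination and does not mention the AE Log. Section 9.3 also relies on PI judgement and lets participants stop, and stopping or suspending treatment is a separate safety outcome. At most, documentation is missing.
- **Laboratory changes are lost.** In hospital they are captured as safety endpoints and graded under SAP 10.5. Protocol 7.8 ends safety assessments at discharge, so this route is limited to participants with blood results.
- **Recording varies by site.** Nothing shows this. Table 13 is an empty shell, and a serious event could properly fill one of the four rows. Uneven recording is a risk that follows from conflicting instructions.

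**Conclusion.** The point holds in a limited form. Section 9.2 has no relatedness exception for eleven symptoms and is silent on those that become serious. It conflicts with the AE and AR definitions in 9.1, and with a SAP table that has rows for four barred terms but no handling rule. Following the plan exactly leaves non-serious drug-related cases without an AE Log entry or causality assessment, so AE incidence and the Poisson comparison under-count tolerability events.

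The certain extent is four preferred terms, with up to nine more by judgement, three of which have a laboratory route. The number of events lost cannot be derived from the documents. With blinding and site-stratified randomisation, recording should not differ systematically by arm: events are lost and absolute differences shrink towards zero. This rests on recording being equally incomplete in both arms.

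The conflict within 9.2 over serious hyperkeratosis, infection or dental events is a separate ambiguity. It calls for reconciliation, and it is not evidence that such events go unreported.

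**What to change.** **Protocol 9.2.** Reconcile it with 9.1 and 9.3. Limit the exemption to listed symptoms that are non-serious and not judged related to trial drug, so that all others are recorded as AEs. State that serious events of special interest are reported as SAEs, which removes the conflict between the opening and closing sentences. A test of worsening over baseline should not be added: the screening history in 7.8 takes only the approximate day of symptom onset, and the schedule in Appendix 4 has no symptom grading.

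**SAP 10.2 and Table 13.** Flag the exempted terms as incompletely ascertained, and state whether entries for them already in the AE Log are included in the summaries and the Poisson comparison.

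**Cost.** A few more AE Log entries, each needing a relatedness judgement. Protocol 10.1 expected recruitment to finish by the end of January 2021, and SAP version 2 is dated 05-04-2021. If recruitment is complete, the SAP change is the usable part and costs only table wording, but it discloses the gap without recovering lost events.
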